10.3.1. Definition of AE

AE Definition

• An AE is any untoward medical occurrence in a patient or clinical study participant, temporally associated with the use of study intervention, whether or not considered related to the study intervention.• NOTE: An AE can therefore be any unfavorable and unintended sign (including an abnormal laboratory finding), symptom, or disease (new or exacerbated) temporally associated with the use of study intervention.

AE Definition

• An AE is any untoward medical occurrence in a patient or clinical study participant, temporally associated with the use of study intervention, whether or not considered related to the study intervention.• NOTE: An AE can therefore be any unfavorable and unintended sign (including an abnormal laboratory finding), symptom, or disease (new or exacerbated) temporally associated with the use of study intervention.

Events Meeting the AE Definition

• Any abnormal laboratory test results (hematology, clinical chemistry, or urinalysis) or other safety assessments (eg, ECG, radiological scans, vital sign measurements), including those that worsen from baseline, considered clinically significant in the medical and scientific judgment of the investigator (ie, not related to progression of underlying disease).• Exacerbation of a chronic or intermittent preexisting condition including either an increase in frequency and/or intensity of the condition.• New conditions detected or diagnosed after study intervention administration even though it may have been present before the start of the study.• Signs, symptoms, or the clinical sequelae of a suspected drug-drug interaction.• Signs, symptoms, or the clinical sequelae of a suspected overdose of either study intervention or a concomitant medication. Overdose per se will not be reported as

an AE/SAE unless it is an intentional overdose taken with possible suicidal/self harming intent. Such overdoses should be reported regardless of sequelae.

Events Meeting the AE Definition

- Any abnormal laboratory test results (hematology, clinical chemistry, or urinalysis) or other safety assessments (eg, ECG, radiological scans, vital sign measurements), including those that worsen from baseline, considered clinically significant in the medical and scientific judgment of the investigator (ie, not related to progression of underlying disease).
- Exacerbation of a chronic or intermittent preexisting condition including either an increase in frequency and/or intensity of the condition.
- New conditions detected or diagnosed after study intervention administration even though it may have been present before the start of the study.
- Signs, symptoms, or the clinical sequelae of a suspected drug-drug interaction.
- Signs, symptoms, or the clinical sequelae of a suspected overdose of either study intervention or a concomitant medication. Overdose per se will not be reported as an AE/SAE unless it is an intentional overdose taken with possible suicidal/self-harming intent. Such overdoses should be reported regardless of sequelae.

Events NOT Meeting the AE Definition

- Any clinically significant abnormal laboratory findings or other abnormal safety assessments which are associated with the underlying disease, unless judged by the investigator to be more severe than expected for the participant's condition.
- The disease/disorder being studied or expected progression, signs, or symptoms of the disease/disorder being studied, unless more severe than expected for the participant's condition.
- Medical or surgical procedure (eg, endoscopy, appendectomy): the condition that leads to the procedure is the AE.
- Situations in which an untoward medical occurrence did not occur (social and/or convenience admission to a hospital).
- Anticipated day-to-day fluctuations of preexisting disease(s) or condition(s) present or detected at the start of the study that do not worsen.

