2.3. Benefit/Risk Assessment

PF-06755347 is not expected to provide any clinical benefit to healthy participants but it may provide a transient increase in platelet count in participants with persistent or chronic ITP. This study is designed primarily to generate safety, tolerability, and pharmacokinetic data that will support further clinical development.

PF-06755347 has been shown to cause transient elevation in pro-inflammatory cytokines. Symptoms associated with CRS vary greatly and may be difficult to distinguish from other conditions. The more common symptoms include fever, nausea, headache, tachycardia, hypotension, rash and shortness of breath. The severity of symptoms can be mild to life threatening and thus there should be a high suspicion for CRS if these symptoms occur. Cytokines will be analyzed to determine if cytokine elevation consistent with CRS is observed (see [Section 10.10](#)). The severity of CRS will be assessed according to the most

recent consensus grading from the American Society for Transplantation and Cellular Therapy (ASTCT).²

For study participants with ITP, there is an increased risk of procedure-related bleeding/bruising from subcutaneous injections, mitigated by the lower bound of platelets in the eligibility criteria. An increased risk of thrombosis has also been reported in ITP.¹⁵ High dose single IV administration of PF-06755347 may transiently lower platelet counts in healthy participants, while repeat IV administration in non-clinical studies may also lower platelet counts. The predicted C_{max} with SC administration in ITP participants is approximately 6 fold lower than observed C_{max} at 1 mg/kg at which the reduction in platelet count was observed in healthy participant (see [Table 6](#)). More detailed information about the known and expected benefits and risks and reasonably expected adverse events of PF-06755347 may be found in the investigators brochure, which is the SRSD for this study.

Each study site should have a COVID-19 risk mitigation policy (RMP), which documents the site's COVID-19 virus testing strategy for participants and staff, social distancing measures, and management of COVID-19-like symptoms.

To account for the widespread deployment of COVID-19 vaccine during the COVID-19 pandemic, the benefit/risk analysis has assessed both the impact of PF-06755347 on risk of COVID-19 disease in study participants who may become infected with SARS-CoV-2 and the efficacy of COVID-19 vaccines.

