6.6. Dose Progression

The participants within each cohort will be dosed using a sequential dosing scheme. For all cohorts, a single participant will be dosed at a given time, followed by a minimum of 72-hour (for IV) and 96-hours (for SC) safety monitoring period. In total there will be a minimum of 96 hours between each IV participant dosed and 120 hours for each SC participant dosed.

The following rules will be applied when considering dosing of the next participant in the cohort.

Sequential dosing may **proceed** only if no adverse events are reported OR all of the following criteria are met:

1. Any pro-inflammatory events are < Grade 2 Per CTCAE criteria in [Appendix 9](#).
2. All other adverse events are deemed mild or moderate in severity, regardless of relatedness.
3. Any laboratory, ECG or vital sign changes are considered not clinically significant.
4. No other pause or stop criteria are met.
5. For participants with ITP, in addition to the above criteria, no participant has greater than a 30% decrease in platelet count – defined from the immediate pre-dosing platelet count to the lowest postdosing platelet count. Dose progression will be independent of dose progression from HP cohorts at higher dose levels.

Sequential dosing should be **paused** if any criterion below is met in a participant receiving active drug:

1. Grade 2 (Objective) pro-inflammatory event (vomiting, diarrhea, hypotension or hypoxia) (see [Appendix 9](#)).
2. Adverse event which is considered to be severe (Grade 3 or higher) AND is deemed related to study intervention.
3. A moderate event (Grade 2) AND is deemed related to study intervention not otherwise identified as a proinflammatory event or AE of special interest, that in the opinion of the PI and Sponsor are of concern and warrant further investigation before additional dosing.
4. For participants with ITP, platelet count of <30 x 10⁹/L AND a decrease from baseline ≥30%, or a platelet count decrease from baseline of ≥50%, defined from the immediate pre-dosing platelet count to the lowest post-dosing platelet count, or a bleeding or bruising-related AE CTCAE 4.03 Grade 2 or higher (except metrorrhagia Grade 3 or higher).

Sequential dosing should be **stopped** at the current dose level if any criterion below is met in participant receiving active drug:

1. Grade 3 or greater pro-inflammatory event.
2. Serious adverse event that is deemed related to study intervention.

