8.2.4. Clinical Safety Laboratory Assessments

See [Appendix 2](#) for the list of clinical safety laboratory tests to be performed and the [SoA](#) for the timing and frequency. All protocol-required laboratory assessments, as defined in [Appendix 2](#), must be conducted in accordance with the laboratory manual and the [SoA](#). Unscheduled clinical laboratory measurements may be obtained at any time during the study to assess any perceived safety issues.

The investigator must review the laboratory report, document this review, and record any clinically relevant changes occurring during the study in the AE section of the CRF. Clinically significant abnormal laboratory findings are those which are not associated with the underlying disease, unless judged by the investigator to be more severe than expected for the participant's condition.

All laboratory tests with values considered clinically significantly abnormal during participation in the study after the last dose of study intervention should be repeated until the values return to normal or baseline or are no longer considered clinically significant by the investigator or medical monitor.

If such values do not return to normal/baseline within a period of time judged reasonable by the investigator, the etiology should be identified and the Sponsor notified.

See [Appendix 6](#) for suggested actions and follow-up assessments in the event of potential drug-induced liver injury.

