8.3.7. Disease-Related Events and/or Disease-Related Outcomes Not Qualifying as AEs or SAEs

Not applicable.

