10.3.2. Definition of SAE

If an event is not an AE per definition above, then it cannot be an SAE even if serious conditions are met (eg, hospitalization for signs/symptoms of the disease under study, death due to progression of disease).

An SAE is defined as any untoward medical occurrence that, at any dose:
a. Results in death
b. Is life-threatening The term “life-threatening” in the definition of “serious” refers to an event in which the participant was at risk of death at the time of the event. It does not refer to an event that hypothetically might have caused death if it were more severe.
c. Requires inpatient hospitalization or prolongation of existing hospitalization In general, hospitalization signifies that the participant has been detained (usually involving at least an overnight stay) at the hospital or emergency ward for observation and/or treatment that would not have been appropriate in the physician’s office or outpatient setting. Complications that occur during hospitalization are AEs. If a complication prolongs hospitalization or fulfills any other serious criteria, the event is serious. When in doubt as to whether “hospitalization” occurred or was necessary, the AE should be considered serious. Hospitalization for elective treatment of a preexisting condition that did not worsen from baseline is not considered an AE.
d. Results in persistent disability/incapacity 
• The term disability means a substantial disruption of a person’s ability to conduct normal life functions.• This definition is not intended to include experiences of relatively minor medical significance such as uncomplicated headache, nausea, vomiting, diarrhea, influenza, and accidental trauma (eg, sprained ankle) which may interfere with or prevent everyday life functions but do not constitute a substantial disruption.
e. Is a congenital anomaly/birth defect

f. Other situations:

- Medical or scientific judgment should be exercised in deciding whether SAE reporting is appropriate in other situations such as important medical events that may not be immediately life-threatening or result in death or hospitalization but may jeopardize the participant or may require medical or surgical intervention to prevent one of the other outcomes listed in the above definition. These events should usually be considered serious.

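### In the ITP cohorts, bleeding or bruising that a site judges to be expected ITP may not be recorded as an AE, and may then miss the bleeding pause criterion, the any-SAE cohort pause and the primary safety data

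*Protocol*

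**What the plan says.** - **AE definition (Protocol 10.3.1).** The list of events that are not AEs includes "The disease/disorder being studied or expected progression, signs, or symptoms of the disease/disorder being studied". The sentence carries an exception: "signs, or symptoms of the disease/disorder being studied, unless more severe than expected for the participant's condition". The list of events that are AEs includes "Exacerbation of a chronic or intermittent preexisting condition including either an increase in frequency and/or intensity of the condition".
- **SAE definition (10.3.2).** Of an event that is not an AE, it says that "it cannot be an SAE even if serious conditions are met (eg, hospitalization for signs/symptoms of the disease under study".
- **Disease-related events (8.3.7).** The section for disease-related events that do not qualify as AEs reads "Not applicable".
- **ITP pause rule (6.6, pause criterion 4).** Two limbs use platelet counts. The third is worded "or a bleeding or bruising-related AE CTCAE 4.03 Grade 2 or higher", with a higher grade for metrorrhagia. Pause criteria 2 and 3 require relatedness to study intervention; criterion 4 does not.
- **SAE rules.** Section 6.1.1.2 pauses the whole cohort for any SAE in a participant on active treatment until the PI and the sponsor have assessed causality. Stop criterion 2 in 6.6 requires a related SAE.
- **Risk statements.** Section 2.1.1 gives bleeding as the main clinical concern in ITP. Section 2.3 names procedure-related bleeding and bruising as a risk for ITP participants and notes: "High dose single IV administration of PF-06755347 may transiently lower platelet counts in healthy participants".

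**The concern.** Leaving expected disease signs out of the AE data does little harm when those signs differ from the risks of the drug, or when a control group shows the background rate. Neither holds in Cohorts 13 and 14. Bleeding is a sign of the disease and also a safety concern for the participant, and the cohorts are open-label without placebo.

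The bleeding limb of pause criterion 4 asks nothing about cause. The AE definition brings attribution back one step earlier: the site may decide that a bleed is expected ITP before anyone has to treat it as an AE. The SAE route has the same problem. The pause in 6.1.1.2 exists so that the PI and the sponsor can assess causality, but an event classed as a non-AE cannot start that process, nor the 24-hour reporting in 8.3.1.1.

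Safety and tolerability is the primary objective, and AEs are among the primary endpoints (Section 3). Under 6.7 the second ITP cohort opens only when the first ITP dose is deemed safe and tolerable. Missing bleeding events would push that judgement in the favourable direction.

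**Working it through.** The plan gives no figure to reproduce here: Section 9.2 reports no formal sample size calculation. The check is mainly textual.

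**1. Follow one event.** Take an ITP participant with Grade 2 bruising or epistaxis away from the injection site after dosing, with a platelet count that meets no pause threshold. Section 10.3.1 poses two questions. Is the event more severe than expected for this participant? Is it an increase in frequency or intensity of the condition?

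- *Yes to either:* it is an AE, the bleeding limb is met, and sequential dosing should pause.
- *No to both:* it is not an AE. As worded, the bleeding limb is not met. By 10.3.2 the event cannot be an SAE, so the 6.1.1.2 pause is not met either, and the event is absent from the AE data.

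The documents do not define what is expected for ITP. They contain no instruction to record all bleeding in ITP participants as AEs. SAP Sections 6.2.1 and 8.3.4 handle only what has been recorded as an AE and add no separate bleeding data.

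**2. Which rules depend on AE status?**

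| Rule | Trigger | Depends on AE status? |
|---|---|---|
| 6.6 pause criterion 4, bleeding limb | Bleeding or bruising AE, Grade 2 or higher | Yes |
| 6.1.1.2 cohort pause | Any SAE on active treatment | Yes, through 10.3.2 |
| 6.6 stop criterion 2 | Related SAE | Yes, but also needs relatedness |
| 6.6 pause criterion 4, platelet limbs | Count below 30 with a fall of at least 30%, or a fall of at least 50% | No |

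**3. Platelet limbs over the eligible range.** Baseline is 30 to 75 × 10⁹/L (5.3). A pause is reached if the count is at most 0.5 × baseline, or is below 30 and at most 0.7 × baseline.

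| Baseline (× 10⁹/L) | 0.7 × baseline | 0.5 × baseline | Pause reached at |
|---|---|---|---|
| 30 | 21 | 15 | ≤ 21 |
| 40 | 28 | 20 | ≤ 28 |
| 50 | 35 | 25 | < 30 |
| 60 | 42 | 30 | ≤ 30 |
| 75 | 52.5 | 37.5 | ≤ 37.5 |

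At each of these baselines a count-based trigger exists that needs no AE.

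**4. Size.** The ITP cohorts have 3 to 6 participants each (9.2), at most 12 combined (4.1). One unrecorded event is 1/6 = 17% to 1/3 = 33% of a cohort.

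As an illustration only, let p be the true risk of Grade 2 or higher bleeding per participant and q the share of such events recorded as AEs. Neither is in the documents, and participants are taken as independent. The chance that the bleeding limb is met at least once among n participants is 1 − (1 − pq)ⁿ.

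| p = 0.2 | q = 1 | q = 0.5 | q = 0.25 |
|---|---|---|---|
| n = 3 | 1 − 0.8³ = 0.488 | 1 − 0.9³ = 0.271 | 1 − 0.95³ = 0.143 |
| n = 6 | 1 − 0.8⁶ = 0.738 | 1 − 0.9⁶ = 0.469 | 1 − 0.95⁶ = 0.265 |

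For n = 6 and p from 0.1 to 0.3, the chance runs from 0.469 to 0.882 at q = 1 and from 0.265 to 0.623 at q = 0.5.

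**The case against.** The strongest reply is that the exceptions will catch most events that matter. Section 5.4 excludes bleeding that needed evaluation or treatment in the 4 weeks before screening, and current bleeding that needs treatment. Section 2.1 selects participants with no acute need for therapy. Against that background a new Grade 2 bleed would often count as an exacerbation or as more severe than expected. This stands and reduces the gap. It does not close it, because the decision rests on an undefined expectation, judged at the site in an unblinded cohort.

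Second, pause criterion 4 was written for ITP and grades bleeding AEs, so its authors presumably meant ITP bleeding to be recorded. Section 8.3.7 can be read the same way, as exempting nothing. That supports the intent, but Appendix 3 still says otherwise.

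Third, other safeguards remain. Each participant's 96-hour data are reviewed before the next is dosed (4.1), an external reviewer sits on the dose escalation subteam (2.1), other findings can halt escalation (6.7), and treatments are recorded with their indication (6.5). All true; none makes the bleed an AE.

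Three stronger readings are tempting and are not supported:

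- *Platelet falls escape the pause rule.* Working step 3 shows that the platelet limbs act on counts, and the synopsis has ITP counts listed and summarized. Section 8.2.4 ("Clinically significant abnormal laboratory findings are those which are not associated with the underlying disease", with its own severity exception) can affect only whether a fall is also coded as an AE. The opening alternative of the proceed rule in 6.6, that no AEs are reported, might be parsed to bypass the platelet proceed criterion. That criterion is worded as an addition for ITP participants, so this point does not rely on that parsing.
- *Injection-site bruising is lost.* Section 6.8 counts ecchymosis at the site as an injection site reaction, 8.3 assesses these reactions within AEs, and Table 3 schedules repeated site assessments.
- *The related-SAE stop rule is disabled.* An event attributed to expected ITP would probably not be judged related anyway, so the exclusion adds little there.

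**Conclusion.** The point holds for bleeding and bruising away from the injection site in ITP participants. A site that follows Appendix 3 may leave such an event out of the AE record. It may then miss one limb of one pause criterion, the any-SAE cohort pause and the primary safety data. This is a gap between definitions that should agree; it does not disable the ITP dose-progression rules as a whole.

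Its reach is at most 12 participants, and only those with a bleed judged both expected and not worsened. The documents give no rate for that, so the probabilities above show direction and scale under assumed p and q and are not estimates for this trial. The cohorts are small and a single qualifying AE is enough to pause dosing, so one event classed the other way can change the outcome. Table 4 lists both ITP cohorts as not yet done, so the text can be corrected before any ITP participant is dosed.

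**What to change.** Reconcile 10.3.1, 10.3.2, 8.3.7 and the bleeding limb of 6.6. State in Appendix 3 that, in the ITP cohorts, every post-dose bleeding or bruising event is recorded as an AE, and as an SAE if a seriousness criterion is met, whether or not it is attributed to ITP. Causality is then assessed separately. Cross-refer to this statement from 8.3.7 and repeat it in the CRF completion guidance. The pause and stop criteria and their thresholds stay as they are.

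The cost is a few sentences in an amendment and a somewhat higher reported AE count in at most 12 participants.

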10.3.2. Definition of SAE

If an event is not an AE per definition above, then it cannot be an SAE even if serious conditions are met (eg, hospitalization for signs/symptoms of the disease under study, death due to progression of disease).

An SAE is defined as any untoward medical occurrence that, at any dose:
a. Results in death
b. Is life-threatening The term “life-threatening” in the definition of “serious” refers to an event in which the participant was at risk of death at the time of the event. It does not refer to an event that hypothetically might have caused death if it were more severe.
c. Requires inpatient hospitalization or prolongation of existing hospitalization In general, hospitalization signifies that the participant has been detained (usually involving at least an overnight stay) at the hospital or emergency ward for observation and/or treatment that would not have been appropriate in the physician’s office or outpatient setting. Complications that occur during hospitalization are AEs. If a complication prolongs hospitalization or fulfills any other serious criteria, the event is serious. When in doubt as to whether “hospitalization” occurred or was necessary, the AE should be considered serious. Hospitalization for elective treatment of a preexisting condition that did not worsen from baseline is not considered an AE.
d. Results in persistent disability/incapacity 
• The term disability means a substantial disruption of a person’s ability to conduct normal life functions.• This definition is not intended to include experiences of relatively minor medical significance such as uncomplicated headache, nausea, vomiting, diarrhea, influenza, and accidental trauma (eg, sprained ankle) which may interfere with or prevent everyday life functions but do not constitute a substantial disruption.
e. Is a congenital anomaly/birth defect

f. Other situations:

- Medical or scientific judgment should be exercised in deciding whether SAE reporting is appropriate in other situations such as important medical events that may not be immediately life-threatening or result in death or hospitalization but may jeopardize the participant or may require medical or surgical intervention to prevent one of the other outcomes listed in the above definition. These events should usually be considered serious.
- Examples of such events include invasive or malignant cancers, intensive treatment in an emergency room or at home for allergic bronchospasm, blood dyscrasias or convulsions that do not result in hospitalization, or development of drug dependency or drug abuse.
- Suspected transmission via a Pfizer product of an infectious agent, pathogenic or non-pathogenic, is considered serious. The event may be suspected from clinical symptoms or laboratory findings indicating an infection in a patient exposed to a Pfizer product. The terms “suspected transmission” and “transmission” are considered synonymous. These cases are considered unexpected and handled as serious expedited cases by pharmacovigilance personnel. Such cases are also considered for reporting as product defects, if appropriate.

